4.9.5 Extent of Exposure

Descriptive statistics (n, mean, standard deviation, median, and range) will be used to summarize the following derived lerociclib exposure variables for each participant in each treatment group. Summaries will be by line of therapy.

- Time on Treatment (days): date of last dose – date of first dose + 1 day,
- Total dose (mg) Received: the sum of total mg taken during the total duration of exposure,
- Average Dose per Day (mg/day): actual cumulative dose intake / total duration of exposure
- Relative Dose Intensity: the amount received divided by the total amount expected on study based in intended dose and time on treatment

Two lerociclib dose level reductions in total are permitted for each participant before discontinuation. The following will be summarized for lerociclib by line of therapy:

- Number and percent of participants with dose interruptions
- Number and percent of participants with a dose reduction
 - Number and percent of lowest daily dose level (200 mg, 150 mg) for each participant requiring a dose reduction
- Number of treatment discontinuations

4.9.6 Data and Safety Monitoring Board (DSMB)

Analyses to be performed in support of the DSMB will be conducted in accordance with the DSMB charter under a separate analysis plan.

4.10 Efficacy Evaluation

4.10.1 Analysis and Data Conventions

Hypothesis testing or other inferential statistical methods will not be used for main analyses of the primary and secondary endpoints.

4.10.1.1 Handling of Dropouts or Missing Data

Data will be presented as observed unless otherwise specified.

Completely or partially missing dates will be imputed per rules outlined in [Appendix 6.2](#).

4.10.1.2 Multiple Comparisons/Multiplicity

No adjustments for multiplicity are required.

4.10.1.3 Visit Windows

Analysis visit windows will be created based on the schedule of assessments in the protocol (Appendix 6.1) as shown below. Any visits outside the visit window will be considered “Unscheduled” and not summarized at a scheduled visit. If multiple records are mapped to the same visit, the one closest to the date of the scheduled assessment will be used. If there is an equal distance from the date of the scheduled assessment, the latest record will be used.

| Visit | Study Day Window |
|------------------|--|
| Screening | [-42, -1] |
| Cycle 1 Day 1 | 1 |
| Cycle 1 Day 15 | [13, 17] |
| Cycle 2 Day 1 | [27, 31] |
| ... | [expected day – 2 days, expected day + 2 days] |
| EOT/ED | [last dose day, last dose + 15 days] |
| Safety Follow-up | [last dose + 25 days, last dose + 35 days] |

For tumor evaluations, the following windows will be implemented:

| Visit | Study Day Window |
|---|--|
| Screening | [-42, -1] |
| Cycle 3 Day 1 | [50, 64] |
| Every 2 cycles (8 weeks) during first 12 months and every 3 cycles thereafter (12 weeks) until EOT/ED | [expected day – 7 days, expected day + 7 days] |
| EOT/ED | [last dose day, last dose + 15 days] |

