- f. Predose and postdose blood samples for lerociclib concentration measurement are to be collected prior to and following the dose of lerociclib on Day 1 and Day 15 of Cycle 1, and on Day 1 of Cycles 2, 3, 4, and 5. The postdose blood sample can be collected between 2 hours and 6 hours (\pm 10 minutes) after the administration of lerociclib. It is important to record the actual time of collection. If the participant is due for a 2- or 6-hour 12-lead ECG assessment, the PK sample may be drawn at the same timepoint but should be obtained after the ECG.
- g. Radionuclide bone scans shall be performed at Screening for all participants every 8 weeks (\pm 7 days) for the first 12 months and every 12 weeks thereafter if initial bone scan is positive for bony lesion. If initial bone scan is negative for bony lesion, bone scan should be done annually or as clinically indicated per Investigator standard of care. All participants with a CR must have a radionuclide bone scan as part of confirmation of the CR. Additional bone scans may be obtained at the discretion of the Investigator, if clinically indicated. Participants with bone-only disease may be followed only with bone scans at the discretion of the Investigator. If CT or bone scan have been done for regular clinical care within 28 days before receiving the first dose of lerociclib, these may be used as baseline scans.
- h. Subsequent cycles may be postponed up to 14 days due to lerociclib interruption. Note that subsequent cycles should start on the original schedule (ie first dosing date).
- i. Participants in the 1L and 2L populations will receive the Investigator's choice of letrozole 2.5 mg daily or fulvestrant 500 mg (dosed according to schedule specified in the protocol).

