9.3.3. Secondary Endpoint(s) Analysis

9.3.3.1. Other Safety Endpoints

Observed values and changes from baseline in vital signs, 12-lead ECG readings, and clinical laboratory parameters will be tabulated at each visit; by visit summaries will be based on scheduled, nominal visits.

Toxicities for clinical laboratory parameters will be characterized according to NCI CTCAE v5.0. Shifts in NCI CTCAE toxicity grades will be summarized. Vital signs and clinically significant findings on physical examination will be listed by participant.

Dose reductions/modifications, interruptions, compliance, and participant exposure will be summarized for each study therapy component, where appropriate.

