4.2.1 Definitions

‘Baseline’ is defined as the last available pre-treatment assessment, where treatment includes the investigational medicinal product (IMP) or any non-investigational medicinal product (NIMP).

‘End of Treatment’ is defined as the value obtained at the EOT visit. If a value for a given parameter was not collected at the EOT visit the last available value collected prior to the EOT visit may be used.

‘End of Study’ (EOS) is defined as the last available post-treatment assessment.

‘Study Day’ will be calculated relative to the date of first exposure to lerociclib. For assessments prior to first exposure, Study Day = Assessment Date – Date of First Exposure. For assessments on or after first exposure date, Study Day = Assessment Date – Date of First Exposure + 1.

The timing of events may also be presented as the Cycle Number and Day (or CXDY), where X is the cycle number and Y is the number of days since the first day of lerociclib treatment in the cycle + 1.

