4.9.3 Clinical Laboratory Evaluation

Chemical laboratory assessments include hematology, clinical chemistry, routine urinalysis, and pregnancy testing. The laboratory tests required by the protocol are detailed in Appendix 10.2 of the protocol.

All laboratory assessments will use local laboratories with results reported on the CRF. As such, laboratory assessments will be summarized by the visit in which the assessment was conducted.

For by-visit summaries, visit windowing will be implemented as specified in Section 4.10.1.3. For across visit summaries (e.g., worst post-baseline value), scheduled, unscheduled and repeat assessments will be considered.

All laboratory tests with values considered clinically significantly abnormal during participation in the study or within 30 days after the last dose of study intervention should be repeated until the values return to normal or baseline or are no longer considered clinically significant by the investigator or medical monitor. When there are repeat laboratory tests conducted on samples collected during the same visit, the last non-missing assessment will be summarized.

Laboratory values for hematology and clinical chemistry will be summarized as raw, change from baseline, and maximum change from baseline (for the participant). Descriptive statistics (for non-categorical data) will be presented by line of therapy for both raw values (n, mean, standard deviation, median, minimum, maximum) and changes from baseline.

A summary of the incidence of abnormal, high, or low values will be created by line of therapy and visit. Shift tables will be created for hematology and clinical chemistry parameters for which normal ranges exist. Shift tables for CTCAE grade shifts from baseline to worst post-baseline will also be presented by line of therapy for hematology and clinical chemistry for low and high shifts separately.

For urinalysis, a summary of the incidence of abnormal, high, and low values will be created. Shift tables will not be created for urinalysis.

A separate summary of findings of potential drug induced liver injury (DILI) will be prepared. The number and proportion of participants meeting one or both of the following criteria at any post-treatment visit will be summarized:

- ALT or AST $3 \times$ ULN and total bilirubin $2 \times$ ULN ($> 35\%$ direct bilirubin) or
- ALT or AST $3 \times$ ULN and international normalized ratio (INR) > 1.5 .

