All participants with a CR must have a radionuclide bone scan as part of confirmation of the CR. Additional bone scans may be obtained at the discretion of the Investigator, if clinically indicated. Participants with bone-only disease may be followed only with bone scans at the discretion of the Investigator. If CT or bone scan have been done for regular clinical care within 28 days before receiving the first dose of lerociclib, these may be used as baseline scans.

- h. Subsequent cycles may be postponed up to 14 days due to lerociclib interruption.
- i. Participants in the 1L and 2L populations will receive the Investigator's choice of letrozole 2.5 mg daily or fulvestrant 500 mg (dosed according to schedule specified in the protocol).
- j. All premenopausal or perimenopausal female participants, and all male participants, must be receiving goserelin for at least 28 days prior to entering the study and will remain on goserelin throughout the study, in accordance with the prescribing information and according to the study site's standard practice. For all study participants (female or male) receiving goserelin, their treatment with goserelin must start at least 28 days before their first dose of lerociclib.
- k. After the Safety Follow-up Visit, survival follow-up should be attempted every 12 weeks for each participant in the long-term Survival Follow-up Phase. Follow-up can be performed via telephone, clinic visits, or by receiving information from a family member or another provider who is administering care. Any anticancer therapies used will be collected where possible.
- l. CT or MRI scans obtained prior to informed consent will not need to be repeated if performed within 28 days prior to dosing with lerociclib.

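### SAP 4.10.1.3 assigns by-visit data through ±2-day windows from first dose, against the protocol's nominal-visit rule, so a Day 1 visit postponed by 3 to 14 days leaves its by-visit table

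*SAP*

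**What the plan says.** **Protocol.** Section 9.3.3.1 covers vital signs, 12-lead ECG and clinical laboratory parameters, and says that "by visit summaries will be based on scheduled, nominal visits". Section 9.3.3.6 summarises the patient-reported outcomes (PROs) on Day 1 of every cycle, or every other cycle for the BR23. It does not use the word nominal.

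**SAP windows.** Section 4.10.1.3 gives Days 13 to 17 for Cycle 1 Day 15, Days 27 to 31 for Cycle 2 Day 1, and for later cycles "expected day – 2 days, expected day + 2 days". Study Day "will be calculated relative to the date of first exposure to lerociclib" (4.2.1), so it does not reset at each cycle. Outside the windows: "Any visits outside the visit window will be considered “Unscheduled” and not summarized at a scheduled visit".

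**SAP laboratory section.** Section 4.9.3 says that "laboratory assessments will be summarized by the visit in which the assessment was conducted". It then says that by-visit summaries use the windows of 4.10.1.3.

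**SAP declaration.** Section 4.13 states that no statistical method in the protocol was changed. The revision history lists the windows as an addition in version 3.0.

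**Timing of cycles.** Footnote h in both schedules says: "Subsequent cycles may be postponed up to 14 days due to lerociclib interruption". Only the protocol's copy continues with "Note that subsequent cycles should start on the original schedule (ie first dosing date"). Protocol 7.1.2 requires assessments to follow the schedule during a temporary discontinuation.

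**The concern.** The SAP has taken the tolerances for holding a visit and used them as the rule for assigning data to a visit. The two serve different purposes. A tolerance tells the site when to see the participant. An assignment rule decides which tabulated visit a real observation belongs to, and it should cope with the departures that the protocol itself permits. Here a permitted postponement is enough to remove a planned Day 1 assessment from its table.

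Change from baseline in laboratory, vital-sign and ECG parameters is a named secondary safety endpoint, and the by-visit tables are a main display of it. Postponement is tied to lerociclib interruption, so the records at risk are not a random subset. Two programmers could also produce different laboratory tables from SAP 4.9.3 as it stands, each able to cite a sentence in support.

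**Working it through.** **Inputs.** Cycle length 28 days (schedule of activities). Study Day 1 is the first lerociclib dose (SAP 4.2.1). Window half-width 2 days, or 7 for tumour evaluations (SAP 4.10.1.3). Postponement up to 14 days (footnote h, both documents).

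**1. Reproduce the SAP's windows.** Expected day of Cycle k Day 1 = 1 + 28(k − 1).
- Cycle 1 Day 15: 15 ± 2 = 13 to 17.
- Cycle 2 Day 1: 29 ± 2 = 27 to 31.
- Tumour evaluation at Cycle 3 Day 1: 57 ± 7 = 50 to 64.

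All three match the SAP.

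**2. Coverage.** From Cycle 2: 5/28 = 17.9% of days. In Cycle 1: Day 1, Days 13 to 17 and Days 27 to 28, so 8 of 28. Over Days 1 to 336: 8 + 11 × 5 = 63, and 63/336 = 18.8%. This describes the gaps; it is not a rate of lost visits.

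**3. Which permitted delays fall outside.** Delays of 1 or 2 days stay in the window. Delays of 3 to 14 days do not, which is 12 of the 14 possible whole-day delays.

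**4. One delay of d days (3 ≤ d ≤ 14) at Cycle 3, followed to Cycle 12.** There are 11 Day 1 visits in Cycles 2 to 12. The Cycle 3 visit falls on Day 57 + d, that is Days 60 to 71. Its window is Days 55 to 59 and the next opens on Day 83.

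| Handling | In own window | Lost |
|---|---|---|
| Assessments kept on the calendar during the hold (Protocol 7.1.2) | 11 of 11 | 0 |
| Visit postponed, original schedule resumed (protocol footnote h) | 10 of 11 | 1 |
| Visit postponed, schedule not resumed | 1 of 11 | 10 |
| Nominal-visit rule (Protocol 9.3.3.1), any of the above | 11 of 11 | 0 |

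**5. Mislabelling.** Without resumption, 14-day delays at Cycles 3 and 5 put Cycle 3 on Day 71 and Cycle 4 on Day 99, both outside any window. Cycle 5 Day 1 falls on 113 + 28 = Day 141, which is the expected day of Cycle 6 (1 + 28 × 5 = 141). It would be tabulated as Cycle 6, and each later visit would likewise move up one cycle.

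**6. Drift without any hold.** Suppose each cycle starts 1 day later than 28 days after the previous one (an assumption about site practice). Cycle 4 then falls on 85 + 3 = Day 88, against a window of 83 to 87. Every visit from Cycle 4 on is out.

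**7. Scope of the textual conflict.** For laboratory data it is explicit: Protocol 9.3.3.1 and the first rule in SAP 4.9.3 oppose SAP 4.10.1.3 and the second rule in 4.9.3. For vital signs and ECG the protocol rule is explicit, while use of the windows is inferred from the general wording of 4.10.1.3, which separates out only tumour evaluations. For PROs the use of the windows is likewise inferred, and the nominal-visit sentence does not cover them.

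**8. Multiple records at a visit.** SAP 4.10.1.3 takes the closest, then the latest. SAP 4.9.4 takes the latest for vital signs. SAP 4.9.3 takes the last non-missing for repeat laboratory tests.

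**The case against.** The strongest defence is that little is lost. Out-of-window laboratory values still count in across-visit summaries, including CTCAE shifts to the worst post-baseline grade, and they are listed. The primary endpoint, incidence of adverse events, uses no visit windows. EQ-5D-5L and GP-5 also have shift tables to the worst value on treatment. No hypothesis is tested. The gaps between windows are days on which no visit is planned, so 5 of 28 says nothing about how many visits are missed. If sites follow Protocol 7.1.2, a hold does not move the assessment. If they follow the protocol's footnote h, only the postponed visit is affected.

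All of this stands, and it limits the consequence to by-visit displays. It does not remove the contradiction between the documents. Nor does it make the SAP consistent with a postponement that its own footnote allows, particularly as that copy omits the return to the original schedule.

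A reader might go further and infer that windowing removes participants with toxicity and so makes the safety profile look better over time. The documents do not support that. Protocol 7.1.2 allows interruption for any reason. Protocol 6.5.1.1 says that neutrophils recover when lerociclib is withheld, so a delayed Day 1 count may be a recovered one, and restoring it could raise the mean. Protocol 4.3 reports that Grade 3 neutropenia without fever required no interruption in the earlier study. No rate of delays beyond 2 days is given, so the number of participants affected cannot be calculated.

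A reader might also infer that windowing the PROs breaches the nominal-visit rule. It does not, because that sentence does not mention them. If the windows are applied to PROs, however, the EORTC scores have only by-visit summaries to rely on.

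**Conclusion.** The SAP is wrong as written, in a limited sense. Its window rule contradicts Protocol 9.3.3.1 for laboratory, vital-sign and ECG summaries and contradicts one of the two rules in its own section 4.9.3. The statement in 4.13 that nothing changed is therefore inaccurate.

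The effect per participant with one delay of 3 to 14 days at Cycle 3 is none, 1 or 10 of 11 Day 1 visits, depending on which scheduling text is followed. The figure of 10 requires that the original schedule is not resumed, contrary to the protocol's footnote h. The loss is linked to lerociclib interruption, but its frequency and the direction of any bias are unknown. The point merits correction because the tables serve named secondary endpoints and the remedy is the method the protocol already states. It does not put the primary safety analysis in doubt.

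**What to change.** 1. In SAP 4.10.1.3 and 4.9.3, base by-visit laboratory, vital-sign and ECG summaries on the nominal visit (cycle and day) recorded in the eCRF, as Protocol 9.3.3.1 requires. Apply the same rule to PROs and say so. Delete the competing sentence in 4.9.3.
2. Use contiguous windows only for records without a nominal visit. The midpoints are Day 22 (between 15 and 29), Day 43 (29 and 57) and Day 71 (57 and 85). Giving each midpoint to the earlier visit yields Days 23 to 43 for Cycle 2 Day 1 and Days 44 to 71 for Cycle 3 Day 1. A record 14 days late then keeps its own cycle (29 + 14 = 43; 57 + 14 = 71).
3. If day windows are kept as the main rule, define the expected day, make the windows contiguous or anchor them to the actual cycle start, and declare the change in 4.13. Contiguous windows counted from first dose would not cure the Day 141 mislabelling; anchoring to cycle start would.
4. Set one multiple-record rule across 4.10.1.3, 4.9.3 and 4.9.4, or state why they differ.
5. The sponsor must reconcile footnote h between protocol and SAP, and with Protocol 7.1.2. This review takes no position on which scheduling rule should apply.

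The cost is SAP wording and modest programming. The downside is a slightly wider spread of actual days within a tabulated visit.

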4.10.1.4 Interim Analyses

No interim analyses are planned for this study.

4.10.1.5 Examination of Subgroups

The uniformity of the treatment effect for the efficacy analysis of Progression-Free Survival (PFS) will be examined for the following subgroups:

1. Age at Enrollment
2. Ethnicity (Not Hispanic or Latino, Other)
3. Race (White, Other)
4. Sex (Female, Male) – While males are allowed in the study it is expected that their enrollment will be very limited. The CSR will note any occurrences when the enrollment of males is too low to allow analyses to run.
5. Childbearing Potential (Yes, No)
6. For Non-Childbearing Potential (Premenarchal, Surgically Sterile, Postmenopausal, Other)
7. Geographic Region
8. Age at Initial Diagnosis
9. Stage at Initial Diagnosis
10. Age at Most Recent Diagnosis
11. Metastasis Sites (Nervous System, Bone, Liver, Respiratory System, Adrenal Gland, Brain, Breast, Other) – may be categorized
12. Histology (Epithelial of ductal origin, Epithelial of lobular origin, Other)
13. Initial Cancer Type [Ductal carcinoma in situ (DCIS), Lobular carcinoma in situ, Invasive ductal carcinoma (ductal breast cancer), Invasive lobular carcinoma, Medullary carcinoma, Mucinous (colloid) carcinoma, Tubular carcinoma, Papillary carcinoma, Metaplastic breast cancer (mBC), Phyllodes tumors, Mammary Paget disease (MPD), Inflammatory breast cancer] – may be categorized
14. Stage at Study Enrollment
15. Reason for Discontinuation of Most Recent Prior Therapy (Progressive Disease, Toxicity, Completion, Unknown, Other, Specify)

Summaries of PFS by line of therapy and subgroup will be produced. No formal statistical analysis will be performed within subgroup.

4.10.2 RECIST Overall Response

The primary evaluation of efficacy endpoints will be based on the final assessment of timepoint Overall Response.

Extent of disease and tumor response will be assessed using Overall Response at each timepoint RECIST v1.1 ([Eisenhauer 2009](#)) as assessed by the Investigator (refer to Section 8.1.1 of the protocol). An Overall Response at each timepoint will be derived algorithmically based on the data entered for Target Lesions, Non-Target Lesions, and New Lesions. However, the Investigator can override this determination based on their clinical judgment of the participant at time of evaluation. In such cases the result of the RECIST algorithm will take precedence in the primary evaluation. The effect of any Investigator overrides will be explored as a sensitivity analysis.

. For participants with measurable disease at baseline the following timepoint responses are possible:

- Progressive Disease (PD)
- Stable Disease (SD)
- Partial Response (PR)
- Complete Response (CR)
- Not Evaluable (NE)

For participants who do not have measurable disease at baseline the following timepoint responses are possible:

- Progressive Disease (PD)
- Non-Complete Response / Non-Progressive Disease (Non-CR/Non-PD)
- Complete Response (CR)
- Not Evaluable (NE)

Once a RECIST v1.1 timepoint response of PD is observed all subsequent RECIST evaluations will not be used in analysis unless otherwise specified [REDACTED]

The primary evaluations of tumor response (ORR, CBR, DOR, and TTR) will be based on the RE set, which is limited to participants with measurable disease at baseline. [REDACTED]

